### *Procedure.*

#### 1. Participants

207 surveys were analyzed obtaining 59 potential participants, dropping out five. 54 participants agreed to participate and gave their written consent. Six participants were excluded due absence of MTrPS, obtaining 48 participants (23 men, 25 women). Principal investigator assigned a number to each participant to perform randomization. Conformation of groups was carried out by simple randomization by dark envelopes. Participants didn't know assigned group and were individually cited in following two weeks to physiotherapy laboratory of SRF to be evaluated.

**Figure 1. Subject recruitment and flow through the study**

## 2. Groups.

Sample was divided by a simple randomization process performed with a random number table, assigned participants to one of two study groups. Sequence of randomization and participants of each group was only known by principal investigator. Working groups were designated as experimental (MEP group, n = 24) and control group (n = 24). None subjects knew the treatment that would be applied. Each participant was evaluated registering their age, BMI and SUTL. Location of MTrP was determined at shortness trapezius muscle, taking as reference a line between superior acromion's midpoint surface and C7 spinous process (PE-AC distance). Algometry and VAS was subsequently applied obtaining the PPT and PI

pre intervention (PPTpre y PIpre). Variables described were compared between groups to assess the homogeneity of them (Table 1). Data reflect the homogeneity of groups at the beginning of the study.

### 3. Pain pressure threshold (PPTpre) and pain intensity (PIpre) preintervention evaluation.

A blinded physiotherapist registered PPT and PI before and after participant's intervention. Evaluation station consisted of a chair and a table with the algometer and VAS. The subjects sat with their backs supported with both feet on the floor. Evaluator proceeded to measure both upper trapezius muscles length manually, choosing the shortest. Subsequently a line was drawn between C7 spinous process and upper acromion midpoint face of ipsilateral shoulder. Most sensitive palpation's point was searched on the line and then marked with a cross measuring distance from C7 to this point. Algometry was applied at selected point exerting a perpendicular pressure until the user referred pain. Participants were instructed to raise slightly contralateral hand when feeling pain in algometry test. A PPT less than 3Kg/cm^2 was recorded as a positive MTrP. This was same protocol used for participants pre-selection where 6 of 54 were excluded. Next pain intensity was assessed with VAS, recording pain magnitude in millimeters produced by algometry. PPTpre and PIpre data were tabulated in Microsoft excel® program sheet.

### 4. Therapeutic ultrasound application.

Participants of both groups received a therapeutic ultrasound treatment. Experimental group received first ultrasound and subsequently MEP, while control group was treated only with ultrasound. Ultrasound intervention protocol was performed in the same way for both groups. Application was performed in an adjoining room by another physiotherapist who didn't know

groups. Treatment was carried out with participant in sitting position applying ultrasound at sensitive point marked by examiner of evaluation station. Ultrasound therapy was delivery at 1MHz, 1.5 Watts/cm^2, 100% duty cycle (SATP: 1.5Watts/cm^2 and SATA:1.5W/cm^2), ERA 5cm^2 and 15 minutes. Once ultrasound intervention was finished, participants of MEP group were taken to microelectrolysis box, while participants of control group returned to evaluation station.

##### 5. Microelectrolysis application.

Microelectrolysis was performed by another physiotherapist. Before intervention, puncture area was cleaned with alcohol. Procedure was performed with latex gloves. Acupuncture needle was introduced perpendicular to demarcated point of trapezius with 0.14mA intensity. Dispersing electrode was placed in external surface of contralateral arm once chosen trapezius muscle. Inside tissue intensity was raised to 0.6mA. Each participant was instructed to indicate to physiotherapist appearance of burning, pain or great local pressure in order to pause emission. Emission time was recorded until symptoms appeared, indicating T1 time, pausing emission for 30 seconds. Then a second emission was made until participant referred again discomfort symptoms. Second emission time was recorded as T2, pausing application again for 30 seconds. Third and last emission was delivered for same time obtained for T2 or if discomfort appeared before completing that time.

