## **Material and Methods**

Present design represents a randomized double-blind clinical trial. Study was approved on June 18, 2019 by Eastern Metropolitan Health Service of Santiago (SSMO) ethics committee. Study was registered at [www.clinicaltrials.gov](http://www.clinicaltrials.gov). Participants were divided in two groups assessed in both presences of MTrPS in shorter upper trapezius muscle. It was recording the PPT and PI before and after intervention. Both groups received therapeutic ultrasound as baseline treatment. Experimental group received microelectrolysis additionally. A reassessment of PPT and PI was done on day one, three and seven post intervention.

*Subjects.* forty-eight healthy volunteers were recruited (23 men, 25 women, average age 22 years). Participants were students of Science Rehabilitation Faculty (SRF) of Andrés Bello University, Santiago de Chile. Number of participants was selected by convenience. An invitation was extended to students through formal communication channels (mailing), student representatives and social networks, summoning two hundred and seven potential participants. Selection was based on a survey whose first part was structured in relation to general demographic participant's data, including name, age, sex, body mass index (BMI), career year, and personal information contact (e-mail and cell phone number). Second part of survey consisted of closed questions constructed by eligibility criteria. Inclusion criteria considered participants over 18 years old, students of SRF and positive hypersensitive MTrPs. Exclusion criteria include neck or shoulders pathologies in the last 6 months (as fractures, sprains, tendinopathies, dislocations or muscle tears), cervical pain, sensitivity alterations such as hypesthesia, anesthesia or hyperesthesia in neck, shoulders and/or arms, wounds or skin alterations in shoulder as psoriasis, scars or keloids, fear to electrotherapy application and analgesic pharmacological treatment at recruitment time (non-steroidal anti-

inflammatory or steroidal drugs). Elimination criteria considered non-tolerance electrotherapy intervention and non-completion of evaluation protocol (attendance at all scheduled sessions). Demographic data were tabulated in Microsoft excel® 2016 program (Table 1, characterization of study groups).

Variable	MEP (n = 24)	Control (n = 24)	p-value	Sample distribution

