##### 6. Pain pressure threshold (PPTpre) and pain intensity (PIpre) postintervention evaluation.

Completing intervention, participants returned to evaluation station. Evaluator repeated the same assessment protocol made before ultrasound and MEP application, recording PPT and PI postintervention. Variables PPTdiff1-1 and PIdiff1-1 were created based on differences

between algometry and pain intensity measurements before and after intervention. Participants were cited for a reevaluation on day three and seven obtained variables PPT2, PI2, PPT3 and PI3. This allowed to create PPTdiff2-1, PPT3-1, PI diff2-1 and PI diff3-1 variables, that represented differences obtained between the measurements of days three and seven with those obtained on day one before intervention.

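### Evaluator blinding after treatment is asserted but not protected: the measured point is swabbed and needled in the MEP arm only, with no concealment or blinding check described.

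*Protocol*

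**What the plan says.** Material and Methods labels the design: "Present design represents a randomized double-blind clinical trial". Procedure 3 describes one assessor: "A blinded physiotherapist registered PPT and PI before and after participant's intervention". That evaluator chooses and marks the site: "Most sensitive palpation's point was searched on the line and then marked with a cross measuring distance from C7 to this point". The reading is taken there: "Algometry was applied at selected point exerting a perpendicular pressure until the user referred pain".

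Procedure 4 gives ultrasound to both arms at the marked point. Controls then go straight back to the evaluator, while MEP participants first go to a separate box. In that box, under Procedure 5, "Before intervention, puncture area was cleaned with alcohol", and then: "Acupuncture needle was introduced perpendicular to demarcated point of trapezius with 0.14mA intensity". Current runs until the participant reports discomfort.

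Procedure 6 brings everyone back to the same station: "Evaluator repeated the same assessment protocol made before ultrasound and MEP application, recording PPT and PI postintervention". It schedules day-three and day-seven reevaluations without saying who performs them.

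**The concern.** PPT is not read by a machine. The evaluator presses by hand and registers the value when the participant raises a hand. An evaluator who knows the arm can, without intending to, press faster or slower, or read later or earlier, in one arm only. PI is rated on the pain that this press produces, so it is exposed too.

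Participants offer no second layer of protection. There is no sham puncture, and a person in the MEP arm feels a needle and a current. The between-arm comparison therefore leans on the evaluator's blinding. The abstract reports one significant between-arm result, PPTdiff2-1 (day three minus the day-one pre-treatment reading), p=0,0032.

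**Working it through.** **Tracing the steps.** No stated figure depends on this point, so the first check is a comparison of the two arms at the skin site the evaluator sees on return.

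| Step | MEP arm | Control arm | Source |
|---|---|---|---|
| Cross drawn by evaluator | yes | yes | Procedure 3 |
| Baseline algometry at the point | yes | yes | Procedure 3 |
| Ultrasound at the point, 15 minutes | yes | yes | Procedure 4 |
| Alcohol on the point | yes | not described | Procedure 5 |
| Needle through the point | yes | no | Procedures 4 and 5 |
| Cover, sham or matched skin preparation | not described | not described | - |
| Same evaluator re-examines and presses, day one | yes | yes | Procedure 6 |

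The arms differ at the site in two ways, the swab and the puncture, and the evaluator inspects and palpates there afterwards.

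**How much an evaluator shift could matter (illustration).** Inputs from the document: n = 24 per arm; baseline SD of PPT 0,2 in each arm (Table 1); p=0,0032 (abstract). Assumed: a two-sided t-test at 5% with 46 degrees of freedom, an SD of change of 0.2 to 0.4 Kg/cm2 (none is printed), and the size of the shift.

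- Standard error = SD × √(2/24): 0.0577 for SD 0.2 and 0.1155 for SD 0.4.
- p = 0.0032 corresponds to t = 3.11, a standardised difference of 3.11 × √(2/24) = 0.90, or 0.18 to 0.36 Kg/cm2.
- With no true effect, the rejection rate comes from the noncentral t distribution with noncentrality shift/SE.
- With the shift taken out of the reported result, t becomes 3.11 − shift/SE.

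| Shift (Kg/cm2) | shift/SE, SD 0.4 to 0.2 | Error rate instead of 5% | p after removing the shift |
|---|---|---|---|
| 0.02 | 0.17 to 0.35 | 5% to 6% | 0.005 to 0.008 |
| 0.05 | 0.43 to 0.87 | 7% to 14% | 0.010 to 0.030 |
| 0.1 | 0.87 to 1.73 | 14% to 40% | 0.03 to 0.17 |

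**A second route to the SD.** Taking the SD of change as 0.2 × √(2(1 − r)) with r assumed at 0.3 to 0.7 gives 0.237 to 0.155 Kg/cm2. By the normal approximation, a 0.05 shift then gives an error rate of 11% to 20%, and a 0.1 shift gives 31% to 61%. For PI, with a pooled baseline SD of √((13.6² + 15.1²)/2) = 14.37 mm and the same r, a 5 mm shift gives about 17% to 34%.

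**The case against.** The protocol states that the evaluator was blinded, and nothing in it says that a 0.3 mm needle left a mark or that anyone saw one. That stands: the text supports an unprotected claim of blinding, and a reader who infers that the evaluator was in fact unblinded goes further than the document does.

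Three other inferences also fail.

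- **A smeared cross as a giveaway.** Both arms have ultrasound at the mark for 15 minutes, so a disturbed cross is not specific to MEP. Repeating the assessment protocol, read plainly, also includes finding and marking the point again.
- **The arm remembered at days three and seven.** This needs the same assessor on those days. Only one evaluator is described, but Procedure 6 names none for the later visits, so carry-over is conditional.
- **Bias explaining the reported day-three result.** Skin cues are freshest minutes after needling, yet the abstract reports a significant difference from control only at the second reevaluation. That pattern does not exclude evaluator bias, but it lends it no support.

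It is also fair to say that the illustration turns on the chosen shift: at 0.02 Kg/cm2 the effect is negligible, and no figure in the document points to 0.1 rather than 0.02. What survives is the core: the puncture and the swab are specific to one arm, the evaluator works on that skin afterwards on day one, and no safeguard is described.

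**Conclusion.** The point holds as a risk created by the procedure as written. It is a matter of trial conduct, not something a protocol would leave to an analysis plan. On day one the evaluator can recognise the arm from the site being measured, and the protocol describes neither protection nor a check. If the same person measures later, that knowledge can carry over.

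The plausible effect ranges from almost nothing to serious, depending on a shift that cannot be estimated from the document and on the assumed test and SD. The figures show sensitivity only, and none of them shows that bias occurred. The conclusion that does not depend on them is that the double-blind label and the unqualified description of the evaluator as blinded are not supported for post-treatment readings.

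**What to change.** **If the procedure can still be changed.** On day one, have a treating physiotherapist already present clean the marked point with alcohol in every participant. Make the site look alike in both arms before return to the evaluator, for example with an identical small cover, and have the evaluator re-measure at the recorded distance from C7. Tell participants not to mention their treatment. Record the evaluator's guess of the arm at the end. State who assesses on days three and seven.

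**Cost.** About a minute per participant, and the cover. Pressing through a cover may alter PPT slightly, so it should be used at the baseline reading too; that the effect is then equal in both arms is likely but not certain on freshly punctured skin. Measuring at the recorded distance replaces the repeat palpation search after treatment, so Procedures 3 and 6 need matching wording. Extending the cover to the later visits could need a second person there. Matching the skin also leaves the different route and delay before return on day one, which remain a cue.

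**If the readings are already taken, as the abstract indicates.** Remove the double-blind label, state that evaluator blinding after treatment was neither protected nor checked, and state that the between-arm PPTdiff2-1 result may include evaluator bias. This costs a few sentences.

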##### 6. Pain pressure threshold (PPTpre) and pain intensity (PIpre) postintervention evaluation.

Completing intervention, participants returned to evaluation station. Evaluator repeated the same assessment protocol made before ultrasound and MEP application, recording PPT and PI postintervention. Variables PPTdiff1-1 and PIdiff1-1 were created based on differences

between algometry and pain intensity measurements before and after intervention. Participants were cited for a reevaluation on day three and seven obtained variables PPT2, PI2, PPT3 and PI3. This allowed to create PPTdiff2-1, PPT3-1, PI diff2-1 and PI diff3-1 variables, that represented differences obtained between the measurements of days three and seven with those obtained on day one before intervention.
